7.4.2 Sensitivity analyses

Sensitivity analyses using different assumptions will be conducted to investigate the potential effect of data handling and the analysis model on the results of the main analysis.

For all sensitivity analyses to data handling assumptions the estimate, two-sided 95% Confidence Interval and p-value of the treatment effect will be represented on the same Forest plot. Tables presenting the results of the sensitivity analyses will be included in Section 16.1.13.1 of the CTR.

Interpretation of sensitivity analyses:

Separate Forest-plots will be produced for the primary and each key secondary endpoint (in Section 15 of the CTR). The consistency of the results of the sensitivity analyses with the primary analysis result will be assessed by checking if the treatment effect estimate of a sensitivity analysis lies inside the confidence interval of the treatment effect of the primary analysis.

The tables corresponding to the Forest-plots will also be performed as part of Section 16.1.13.1 of the CTR.

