Sensitivity 3 ^[2]	based upon the slope (SE) estimates in Placebo patients from the primary analysis model, i.e. in patients from pattern 1 or 2: multiple imputation of missing week 52 data in all patients regardless of treatment group	rate of decline in all patients with missing week 52 data is similar to rate of decline estimated in all Placebo patients (e.g. treatment effect does not persist after trial drug discontinuation)	multiple imputation of missing 52 week data due to death based on the same slope (SE) estimates in all Placebo patients (i.e. in patients from pattern 1 or 2), but truncated ^[3] to force the slope in patients who died to be more severe than in those who survived	Assuming that deaths observed in the trial will likely be related to worsening of SSc, it seems reasonable to assume that the unobserved FVC values should on average be lower than those in patients who did not die prior to week 52 Rate of decline in patients who died before week 52 is similar to rate of decline in the Placebo patients with most severe slopes

[1] Sensitivity analyses 1 and 2 will only be performed if the number of patients in pattern 2 is greater than 10 (from both Nintedanib and Placebo group together for sensitivity analysis 1 and from placebo group for sensitivity analysis 2)

[2] Patients falling into pattern 2 are used as the basis for multiple imputations in sensitivity analyses 1 and 2 but since the number of patients in that pattern may be small, a third sensitivity analysis will be performed to confirm the robustness of the primary analysis results.

[3] If β represents the true slope with $f(\beta) \sim N(\hat{\beta}, \hat{\sigma}^2)$ where $\hat{\beta}$ and $\hat{\sigma}$ are the placebo slope and SE estimates from either patients in pattern 2 or all placebo patients, then sampling for patients who died prior to 52 weeks is restricted to the interval $(-\infty, \hat{\beta}]$ of the truncated distribution $f(\beta)/2$. In this way, it is guaranteed that, on average, the imputed FVC slope for patients who died is steeper than the average slope in patients who survived to week 52.

In addition to the patterns defined in the scope of the multiple imputation, the number (and percentage) of patients in each possible pattern of FVC data will be explored and presented in Appendix 16.1.13.1 of the CTR. Graphs showing FVC data over time in each pattern of monotonic missing data will also be provided in Appendix 16.1.13.1 of the CTR.

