9.2 COMPLEMENTARY INFORMATION ON STATISTICAL MODEL AND SAS CODE

Primary endpoint model (and other rate of decline endpoints):

The key code is given below. Time is defined as duration since first trial drug intake divided by 365.25. Visit is the visit number.

Meanbase corresponds to the overall mean baseline for the endpoint.

```
proc MIXED data=FVC cl method=reml order= formatted covtest;
  CLASS patient visit treatment gender ata;
  MODEL endpoint= gender age height ata fvcbaseline fvcbaseline*time
  treatment treatment*time /solution CL ddfm=KR;
  RANDOM intercept time/ type=un subject=patient;

  ESTIMATE 'Nintedanib' fvcbaseline*time MEANBASE treatment*time 0 1 /
e CL;
  ESTIMATE 'Placebo' fvcbaseline*time MEANBASE treatment*time 1 0 / e
CL;
  ESTIMATE 'Nintedanib 150mg bid - Placebo' treatment*time -1 1 / e CL;
RUN;
```

Primary endpoint subgroup analysis model:

This is the case of subgroups with 2 categories:

```
proc MIXED data=FVC cl method=reml order= formatted covtest;
  CLASS patient visit treatment gender ata subgroup;
  MODEL endpoint= gender age height ata fvcbaseline fvcbaseline*time
  treatment*subgroup treatment*subgroup*time /solution CL ddfm=KR;
  RANDOM intercept time/ type=un subject=patient;

  ESTIMATE 'Nintedanib - Subgroup A' fvcbaseline*time MEANBASE treatment *
subgroup *time 0 0 1 0 / cl e;
  ESTIMATE 'Placebo - Subgroup A' fvcbaseline*time MEANBASE treatment *
subgroup *time 1 0 0 0 / cl e;

  ESTIMATE 'Nintedanib - Subgroup B' fvcbaseline*time MEANBASE treatment *
subgroup *time 0 0 0 1 / cl e;
  ESTIMATE 'Placebo - Subgroup B' fvcbaseline*time MEANBASE treatment *
subgroup *time 0 1 0 0 / cl e;

  ESTIMATE 'Nintedanib - Placebo Subgroup A' subgroup * treatment *time -1
0 1 0 / e CL;
```

```
'Week 52, Subgroup 3'  
0 0 0 0 0 0 0 0  
0 0 0 0 0 0 0 0  
0 0 0 0 0 0 0 0  
0 0 0 0 0 0 0 0  
0 0 0 0 0 0 0 0  
0 0 0 0 0 0 0 0  
0 0 0 0 0 0 0 0  
1 1 -3 1 -1 -1 3 -1,
```

```
'Week 52, Subgroup 4'  
0 0 0 0 0 0 0 0  
0 0 0 0 0 0 0 0  
0 0 0 0 0 0 0 0  
0 0 0 0 0 0 0 0  
0 0 0 0 0 0 0 0  
0 0 0 0 0 0 0 0  
0 0 0 0 0 0 0 0  
1 1 1 -3 -1 -1 -1 3
```

```
/divisor=4 joint elsm cl alpha=0.05;  
RUN;
```

For 2 subgroups, the LSMESTIMATE will write:

```
LSMESTIMATE visit*treatment*subgroup
```

```
'Week 52, Subgroup 1'  
0 0 0 0  
0 0 0 0  
0 0 0 0  
0 0 0 0  
0 0 0 0  
0 0 0 0  
-1 1 1 -1,
```

```
'Week 52, Subgroup 2'  
0 0 0 0  
0 0 0 0  
0 0 0 0  
0 0 0 0  
0 0 0 0  
0 0 0 0  
1 -1 -1 1
```

```

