/divisor=2 joint elsm cl alpha=0.05;
```

Implementation of multiple imputation:

The following steps provide a guidance of how missing FVC data at week 52 will be implemented in patients of pattern 3 and 4 using multiple imputation. Refer to [Table 7.4.2.1.2: 1](#) for the description of patterns and the different sensitivity analyses regarding handling of missing data.

1. Run the MMRM of the primary analysis (either including patients of pattern 2 only for sensitivity analyses 1 and 2 or on all patients for sensitivity analysis 3) to get the slope estimates (SE) by treatment group. Let $\hat{\beta}_D$ and $\hat{\sigma}_D$ denote the slope (SE) estimates in Nintedanib 150 mg and $\hat{\beta}_P$ and $\hat{\sigma}_P$ the slope (SE) estimates in placebo.
2. Let β_D and β_P represent the true slopes in drug and placebo respectively with $f(\beta_D) \sim N(\hat{\beta}_D, \hat{\sigma}_D^2)$ and with $f(\beta_P) \sim N(\hat{\beta}_P, \hat{\sigma}_P^2)$, using the slope (SE) estimates obtained in step 1.
3. Imputation of missing week 52 data in patients of pattern 3:

Multiple impute missing values (1000 imputations per patient). To do so, draw random slopes from the distributions defined in step 2. Considering that the withdrawal of a patient leading to missing data can occur at any time during the study, the timepoint of the last available FVC value has to be taken into account to impute the missing FVC value at 52 weeks.

$$\text{FVC week 52 imputed}_{ij} = \text{last FVC value available}_i + \hat{\beta}_{ij}(\text{time between date of last FVC value available}_i \text{ and planned 52 week timepoint [days]})$$

where i denotes the indicator of the i^{th} patient, j the indicator of the j^{th} imputation and $\hat{\beta}_{ij}$ denotes a random slope sampled from the distribution mentioned in step 3a for the i^{th} patient in the j^{th} imputation. Depending on the sensitivity analysis, use either random slopes drawn from $f(\beta_D)$ for patients randomised to Nintedanib 150 mg in sensitivity analysis 1 or $f(\beta_P)$ for all patients in sensitivity analyses 2 and 3.

4. Imputation of missing week 52 data in patients of pattern 4:

Multiple impute missing values (1000 imputations per patient). To do so, draw random slopes from the truncated distribution $f(\beta_P)/2$ restricted to the interval $(-\infty, \hat{\beta}_P]$ defined in step 2.

See step 3 for further details on how to use these slopes to impute the missing values at week 52.

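### Sensitivity analysis 1 will report too narrow an interval because SAP 9.2 redraws the error of a group mean slope for every patient; the same steps also mix units, miss the stated death assumption and loosen the protocol's trigger

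*SAP*

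**What the plan says.** SAP 7.4.2.1.2 plans three multiple-imputation analyses with 1000 imputations, and SAP 9.2 gives the steps. Step 1 fits the primary model to pattern 2 (stopped drug early, week-52 FVC available) for sensitivities 1 and 2, or to all patients for sensitivity 3. Step 2 sets a normal distribution for each arm's true slope, with the estimate as mean and the SE as SD. Step 3 says to "draw random slopes from the distributions defined in step 2", with the draw indexed by patient and imputation. It multiplies the draw by the time between the last FVC "and planned 52 week timepoint [days" and refers to "a random slope sampled from the distribution mentioned in step 3a". For the model, the same section states: "Time is defined as duration since first trial drug intake divided by 365.25".

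For deaths, step 4 and footnote 3 of Table 7.4.2.1.2: 1 truncate the same distribution at its mean, using "placebo slope and SE estimates from either patients in pattern 2 or all placebo patients". The table gives the assumption for sensitivity 3 as "Rate of decline in patients who died before week 52 is similar to rate of decline in the Placebo patients with most severe slopes", and for sensitivities 1 and 2 in similar words about pattern 2.

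Under SAP 7.4.2, for each data-handling sensitivity analysis the estimate, "two-sided 95% Confidence Interval and p-value of the treatment effect will be represented on the same Forest plot". Consistency is judged by whether the sensitivity estimate "lies inside the confidence interval of the treatment effect of the primary analysis".

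Protocol 7.5.1 permits sensitivities 1 and 2 only when each arm has ten or more subset-2 patients. SAP footnote 1 asks for more than ten in the two arms combined (sensitivity 1) or on placebo (sensitivity 2).

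**The concern.** The SE in step 2 measures uncertainty about one number per arm. Step 3 treats it as independent patient-level spread. A shared error drawn separately for each patient largely cancels in the arm mean, so the between-imputation variance that Rubin's rules need is almost absent. The fitted model does contain patient slope variance and residual error, but neither enters the imputed values.

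In sensitivity 1 each arm borrows its own pattern-2 slope, so the two lost errors do not cancel in the treatment difference. At stake are the interval and p-value shown in Section 15 of the trial report. Sensitivity 1 would look more precise than the primary analysis, and more so as data are lost, while its true error grows.

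Four further points sit in or beside these steps: the time unit, the size of the death penalty, the direction of truncation for mRSS and SGRQ, and the trigger for running sensitivity 1.

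**Working it through.** **Inputs from the plan.** 260 per arm and a 52-week change SD of 245 mL (Protocol 7.7); random intercept and slope model, draw rule and time scale (SAP 7.4.1, 9.2). The protocol's 259 per group for 70 mL at 90% power reproduces (noncentral t: 259; power at 260: 90.3%). The plan gives no SE, dropout rate or pattern-2 size for the sensitivity analyses, so these are assumed below.

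**Why the variance disappears.** Suppose m of an arm's n patients are imputed, with remaining times t_i. The imputed part of the arm mean is Σ b_i t_i / n.
- As written (separate b_i): variance = SE² Σt_i² / n².
- One shared draw: variance = SE² (Σt_i)² / n².
- The ratio is (Σt_i)² / Σt_i², close to m.

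Simulated between-imputation variances agree: 43.0/1.9 = 22.6 for m = 26, and 173.1/3.8 = 45.6 for m = 52. Adding patient slope and residual variation raises 43.0 to 64.5 and 173.1 to 218.2.

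**Coverage of sensitivity 1, assumption set A.** Slope SD 215, residual SD 85, so the change SD is √(215² + 2×85²) = 246. No true effect, balanced random dropout, last visit uniform over weeks 4 to 36, time in years, 1,500 trials per scenario.

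| Pattern 2 per arm | 10% missing | 15% | 20% | 30% |
|---|---|---|---|---|
| 26 | 92.5% | 91.3% | 88.6% | 84.5% |
| 13 | 92.3% | 89.8% | 85.8% | 78.3% |
| 6 | – | 87.0% | – | – |

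With 26 per arm, going from 10% to 30% missing, the reported SE falls from 20.1 to 18.8 mL/yr. The true SD rises from 21.9 to 26.8 and the primary SE from 21.4 to 23.2. Intervals are 8–29% (26 per arm) or 10–37% (13 per arm) narrower than with a full draw, which covers 93.5–94.9%. With 20% against 10% dropout, coverage is 90.9% (26) and 89.0% (13). SD splits of 190/110 and 235/50 at 15% missing give 91.2% and 90.6%.

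**Assumption set B.** Slope SD 200, residual SD 100 (change SD √(200² + 2×100²) = 245), true effect 70 mL/yr, 10 pattern-2 patients per arm, 1,000 trials.

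| Missing | SE as written | Primary SE | True SD | Coverage as written | Full-draw SE | Full-draw coverage |
|---|---|---|---|---|---|---|
| 5% | 19.95 | 20.49 | 19.71 | 95.8% | 20.72 | 96.5% |
| 10% | 19.75 | 20.85 | 20.92 | 94.2% | 21.82 | 96.2% |
| 20% | 19.35 | 21.67 | 24.19 | 88.3% | 25.28 | 95.8% |

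A shorter repeat of set A (300 trials) gave 92.0% (26 per arm, 10% missing) and 88.0% (13 per arm, 20% missing). The full draw gave 94.3–94.7%.

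**Sensitivities 2 and 3 (set A).** Both arms use one placebo slope, so the shared error largely cancels. Coverage as written is 94.5–95.4% and 94.2–95.3%. Their SEs (18.6–20.2) are still below the primary's (21.2–23.2). A full draw makes them conservative (2.1–3.9% rejection).

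**Deaths.** A normal distribution truncated at its mean shifts by √(2/π) × SD = 0.80 × SD.
- Sensitivity 3: SE 15.1–16.4 gives 12–13 mL/yr.
- Sensitivities 1 and 2: SEs of 46, 66 and 99 (26, 13 and 6 placebo patients) give 37, 53 and 79 mL/yr.
- Steeper half of placebo patients: 0.80 × 215 = 172 mL/yr.

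The penalty therefore depends on the number of reference patients, not on how fast steep decliners decline. If 2% die in one arm only, with half a year left, the difference moves by (172 − 12) × 0.5 × 0.02 = 1.6 mL. The rule is written for the lower side only. mRSS and SGRQ are imputed too (SAP Table 7.4.2.3: 1), and for them higher is worse (SAP 5.2.1).

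**Units.** −100 mL/yr × 182 days gives −18,200 mL as written; −100 × 182/365.25 gives −50 mL.

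**Trigger.** The protocol minimum for sensitivity 1 is 10 + 10 = 20 patients; the SAP minimum is 11, with no minimum per arm. Totals of 11 to 19 pass the SAP and fail the protocol. The SAP 9.2 model has 10 fixed effects (intercept, gender, age, height, ATA, baseline, baseline-by-time, treatment, two treatment-by-time) and 4 covariance parameters. SAP Section 4 does not list the change.

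**The case against.** The strongest reply concerns reach. No confirmatory inference depends on sensitivity 1. The SAP judges consistency by the point estimate alone, and in set A that lay inside the primary interval in 98.3–100% of trials. The SAP foresees that pattern 2 may be small and adds sensitivity 3 for that reason; sensitivities 2 and 3 are near nominal. SAP 7.4.2.1.1 gives first importance among the sensitivity analyses to the on-treatment analysis. All of this stands, and it limits the severity.

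Size is also conditional. At 5% missing coverage is intact, and at 10% the two assumption sets differ (92.3–92.5% against 94.2%). The protocol asks patients who stop drug to keep attending, so 30% missing with only 13 retained is an extreme case and should not be the headline.

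The death rule does satisfy footnote 3, which promises only a steeper average, and the protocol's milder wording; its effect is small. The unit slip and the reference to a missing step are clerical, and a result of −18,200 mL would be noticed. For sensitivity 2 the placebo threshold became slightly stricter, and the dropped nintedanib minimum concerns a slope it does not use.

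Calling the SAP 9.2 steps guidance does not remove the main point. Footnote 3 repeats the SE-based distribution, and the SAP gives no other specification. More imputations cannot restore variance that is never drawn.

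**Conclusion.** The concern holds and should be fixed, though it does not threaten the trial's conclusions. As written, sensitivity 1 omits almost all between-imputation variance. The larger cause, when pattern 2 is small, is that the mean-slope draw is not shared; the missing patient-level and residual variation adds to it. Replacing the SE with the slope SD alone would not cure the first part.

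The effect is negligible at 5% missing. At 10% coverage is about 92–94%, and at 20% about 86–89%, with 10 to 26 pattern-2 patients per arm. These figures rest on the assumed variance split, random dropout and pattern-2 sizes. At 10% missing or more, the reported SE lies below both the primary SE and the estimator's true SD in both assumption sets. Under-coverage is shown for sensitivity 1 only.

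The days-for-years error, the reference to a missing step and the looser, unlisted trigger for sensitivity 1 can be read directly from the text. The death rule is a mismatch between the rule and the table's stated assumption, with little numerical effect if deaths are few.

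**What to change.** 1. **Sensitivity 1.** In each imputation draw one mean slope per arm from its normal distribution and use it for all patients imputed from that arm. Then add a patient slope deviation from the fitted between-patient variance, and a residual error. Keep the planned reference-group mean; do not condition on the patient's own on-drug slope.
2. **Sensitivities 2 and 3.** Either use the same code and accept mild conservatism, or keep the current draw and state that their intervals leave out missing-data uncertainty.
3. **Deaths.** Either truncate the patient-level placebo slope distribution, or restate the table's assumption as steeper on average than the mean placebo slope. State that truncation for mRSS and SGRQ is on the upper (worsening) side.
4. **Wording of step 3.** Express time as days/365.25 and correct the reference to step 3a.
5. **Trigger.** Restore ten or more pattern-2 patients in each arm, or list and justify the change in SAP Section 4.

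The cost is SAP wording and modest reprogramming. Across the 26- and 13-per-arm set A scenarios with balanced dropout, sensitivity 1 intervals become about 9–58% wider, the upper end being the extreme 30%-missing case. The primary analysis does not change.

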9.3 ADDITIONAL ANALYSIS FOR REGIONAL SUBMISSIONS

For the Japanese submission, the analyses will be conducted according to “Format for Preparing the Common Technical Document for Submission of New Drug Applications to Reduce Total Review Time” (21).

For the analysis due to local regulatory submission, the following subsets are defined (4).

Some outputs from CTR Section 15 will be selected for the subsets defined in Table 9.3: 1. Due to small sample size of some subsets, some tables might be skipped. The same analyses models as defined for the overall population will be used (please refer to Section 7.4.1). In the event of non-convergence, the same methods than the ones described in Section 7.4.1 will be used to overcome the issue.

Table 9.3: 1 Patient subsets definition for local regulatory submission in Asia

Category	Patient subset
Local	
 • Japan • China 
The patients in each local site and Asian race will be included (e.g. Japan: Site in Japan and single race is Asian). If Asian race will be "Multiple" and multiple responder will be "Asian & xxx", the patient will be handled as "Asian". (e.g. Japan: Site in Japan and multiple race is Asian & White.)

East Asia	
 • East Asian countries 
The patients from East Asian countries or region (i.e. Japan and China) with Asian race. Asian race definition is same definition in local category.

India	
 • India 
The patients in any race from India sites will be included.

These subset analyses will not be produced as part of the CTR appendix and will not be described in the text of the CTR (9). The details will be handled in another document (cumulative SAP).

9.4 LIST OF BI CUSTOMISED DRUG GROUPINGS OF INTEREST

Customized drug groupings of interest for this trial are listed in Table 9.4: 1.

Table 9.4: 1 Customized drug grouping of interest

CT grouping name	Type of grouping
Antiarrhythmics	SDG
Antidiarrheal	ATC4 ('A07DA')
Antiemetics and antinauseants	SDG, excluding drugs from the Corticosteroids SDG
Antihypertensives	SDG
Anti-infectives	SDG
Antithrombotic drugs	SDG
Corticosteroids	SDG
Drugs interacting with CYP3A	SDG
Disease-modifying antirheumatic drugs (DMARDs)	SDG
Diuretics	SDG
Drugs for gastric acid related disorders	SDG
Drugs for obstructive airway diseases	SDG
Drugs used in pain therapies	SDG
Hormone replacement therapy	SDG
Immunosuppressant drugs	Sub-SDG (from Immunomodulators SDG)
Monoclonal antibodies	SDG
Nonsteroidal anti-inflammatory drugs (NSAIDs)	SDG
Drugs interacting with P-glycoprotein (P-gp)	SDG

Table 9.4: 1 Customized drug grouping of interest (cont'd)

CT grouping name	Type of grouping
Phosphodiesterase (PDE) inhibitors	SDG
Statins	SDG

WHO-DD version used: 18.MAR

9.5 SPECIFICATION OF RESTRICTED AND FORBIDDEN CONCOMITANT THERAPIES

Medications reviewed as potential IPVs were selected based on Table 9.5: 1

Table 9.5: 1 Restricted and forbidden concomitant therapies

Type of medication	Category of drugs	ATC/PN
Prohibited medications	Pirfenidone	PN='Pirfenidone'
	Nintedanib (outside of the trial)	L01XE
	Other investigational drugs	PN='Investigational drugs'
Restricted medications	Full dose therapeutic anticoagulation	B01AA, B01AB, B01AF, B01AE, B01AD, B01AX
	Antiplatelet therapies	B01AC, B01AX
	Mycophenolate mofetil/ sodium / MYCOPHENOLIC ACID	PN='Mycophenolate mofetil' or PN='Mycophenolate sodium' or PN='MYCOPHENOLIC ACID'
	Methotrexate	PN='Methotrexate' or PN='Methotrexate sodium'
	Azathioprine, potassium para-aminobenzoate	L04AX
	Cyclophosphamide	PN='Cyclophosphamide'

Table 9.5: 1 Restricted and forbidden concomitant therapies (cont'd)

Type of medication	Category of drugs	ATC/PN
	Prednisone > 10mg /day	H02AB
	Hydroxychloroquine, colchizine, D-penicillamine, sulfasalazine	PN=' Hydroxychloroquine' or PN=' colchizine' or PN=' penicillamine' or PN=' sulfasalazine
	Rituximab, tocilizumab, abatacept,leflunomide, tacrolimus, newer anti-arthritic treatment like tofacitinib	L04AC, L04AA, D11AH, L04AD, L04AA

9.6 LIST OF POTENTIAL TERMS FOR HEPATIC INJURY DERIVATION

Table 9.6: 1 shows the list of potentially relevant MedDRA preferred terms to support the derivation of a potential hepatic injury:

Table 9.6: 1 List of potentially relevant MedDRA preferred terms

Symptom	MedDRA
Vomiting	PT Vomiting
Fatigue	PT Fatigue
Nausea	PT Nausea
Right upper abdominal quadrant pain or tenderness	HLT "Gastrointestinal and abdominal pains (excl oral and throat)"
Fever	PT Fever
Rash	BlcMQ skin rash (narrow)

9.7 LIST OF TERMS INCLUDED IN STROKE PHARMACOVIGILANCE ENDPOINT

This list is based on MedDRA Version 21.0. Updates will be only maintained in BIRDS as specified in [Section 7.8.1.4](#).

The following MedDRA Preferred Terms will be used to define stroke pharmacovigilance endpoint:

Amaurosis fugax
Amyloid related imaging abnormalities
Amyloid related imaging abnormality-microhaemorrhages and hemosiderin deposits
Amyloid related imaging abnormality-oedema/effusion
Basal ganglia haematoma
Basal ganglia haemorrhage
Basal ganglia stroke
Basilar artery occlusion
Basilar artery perforation
Basilar artery thrombosis
Brachiocephalic artery occlusion
Brain stem embolism
Brain stem haematoma
Brain stem haemorrhage
Brain stem infarction
Brain stem ischaemia
Brain stem stroke
Brain stem thrombosis
Brain stent insertion
Carotid aneurysm rupture
Carotid arterial embolus
Carotid artery occlusion
Carotid artery perforation
Carotid artery thrombosis
Central nervous system haemorrhage
Cerebellar artery occlusion
Cerebellar artery thrombosis
Cerebellar embolism
Cerebellar haematoma
Cerebellar haemorrhage
Cerebellar infarction
Cerebellar ischaemia
Cerebellar stroke
Cerebral aneurysm perforation
Cerebral arteriovenous malformation haemorrhagic
Cerebral artery embolism
Cerebral artery occlusion
Cerebral artery perforation
Cerebral artery restenosis

Cerebral artery thrombosis
Cerebral haematoma
Cerebral haemorrhage
Cerebral haemorrhage foetal
Cerebral haemorrhage neonatal
Cerebral infarction
Cerebral infarction foetal
Cerebral ischaemia
Cerebral microembolism
Cerebral thrombosis
Cerebral vascular occlusion
Cerebrovascular accident
Delayed ischaemic neurological deficit
Embolic cerebral infarction
Embolic stroke
Haemorrhage intracranial
Haemorrhagic cerebral infarction
Haemorrhagic stroke
Haemorrhagic transformation stroke
Intracranial haematoma
Intracranial tumour haemorrhage
Intraoperative cerebral artery occlusion
Intraventricular haemorrhage
Intraventricular haemorrhage neonatal
Ischaemic cerebral infarction
Ischaemic stroke
Lacunar infarction
Lacunar stroke
Lateral medullary syndrome
Perfusion brain scan abnormal
Perinatal stroke
Periventricular haemorrhage neonatal
Pituitary haemorrhage
Pituitary infarction
Post procedural stroke
Precerebral artery occlusion
Precerebral artery thrombosis
Pseudostroke
Putamen haemorrhage
Reversible ischaemic neurological deficit
Ruptured cerebral aneurysm
Stroke in evolution
Subarachnoid haematoma
Subarachnoid haemorrhage
Subarachnoid haemorrhage neonatal
Subdural haemorrhage neonatal

Thalamic infarction
Thalamus haemorrhage
Thrombotic cerebral infarction
Thrombotic stroke
Transient ischaemic attack
Vertebral artery occlusion
Vertebral artery perforation
Vertebral artery thrombosis

